8 STATISTICAL METHODOLOGY

Listings will be presented in treatment, subject, visit (where applicable), and date (where applicable) order.

8.1 Study Subjects

8.1.1 Subject Disposition

Subject disposition will be summarized on the RAND population.

The number of subjects who completed all treatment period (DBT and DBE), prematurely discontinued either DBT period or DBE period, completed DBT period, DBE period, and the safety follow-up period with the reasons for discontinuation in each period will be summarized. In addition, the number and percentage of the subjects that received placebo treatment in MT-7117-A01 study will be summarized.

The number of subjects who enter screening will be summarized, and the percentage of these subjects who fail to meet entry criteria will be reported for total subjects. Screen failures will be summarized in total and by each reason for screen failure.

8.1.2 Analysis Populations

Analysis populations will be summarized on the RAND population. Analysis populations will be listed on the RAND population.

8.1.3 Protocol Deviations

Protocol deviations including major deviations specified in the blinded blinded data review meeting will be listed on the RAND population.

[figure not shown]
8.1.4 Stratification Registration Errors

In addition, the number of subjects with unmatched stratification registration will be summarized by comparing between IWRS strata data and actual strata from e-Diary data derivation and between IWRS strata data and vendor [REDACTED] report strata on the RAND population.

8.1.5 Demographic and Other Baseline Characteristics

The following demographic and other baseline characteristics will be used.

	Category	Descriptive
Sex	Male, Female	
Age (years)	Adolescent(<18) Adult(18 – 65, >65)	Yes
Height (cm) at screening visit		Yes
Weight (kg) at screening visit	<45 ≥45	Yes
BMI (kg/m2)	[REDACTED]	Yes
Race	White, Black or African American, Asian(Japanese), American Indian or Alaska Native, Native Hawaiian or Pacific Islander, Other	
Country	US, Australia, Canada, Germany, Italy, Japan, Norway, Spain, Sweden, United Kingdom (from IWRS data)	
Region (Randomization stratification factor)	North America, Rest of world (Europe, Japan, Australia) (from IWRS data)	
Ethnicity	Hispanic or Latino, Non-Hispanic or Latino	
EPP/XLP	EPP, XLP	
Protoporphyrin (PPIX level) (mcg/dL)		Yes
Disease duration (years)		Yes
Baseline average daily time to first prodromal symptom (Randomization stratification factor)	[REDACTED]	
Actual baseline average daily time to first prodromal symptom	[REDACTED] [REDACTED]	Yes
Seasonality 1	Randomized in Spring and Summer inclusive, Other	

	(Spring and Summer: between September 1st to February 29 in Australia or between March 1st and August 31th in the other countries)	
Seasonality 2	Week 26 visit in Spring and Summer inclusive, Other (Spring and Summer: the date of Week 26 analysis visit is between September 1st and February 29th in Australia or the date of Week 26 analysis visit is between Mar 1st and August 31th in the other countries)	
Melanin density		Yes
Fitzpatrick skin type	I, II, III, IV, V-VI	
		

Demographic and other baseline characteristics will be summarized on the ITT1, ITT2, SAF1, and SAF2 populations. Demographic and other baseline characteristics will be summarized on the ITT1, ITT2, SAF1, and SAF2 populations by region (North America, Europe, Japan, Australia).

Demographic and other baseline characteristics will be listed on the RAND population.

8.1.6 Medical History

Medical history will be summarized on the SAF1 and the SAF2 populations. In this summary, SOC is sorted by International order; then within SOC, PT is sorted by descending counts under MT-7117 [REDACTED], MT-7117 [REDACTED] or Placebo (switched to [REDACTED], switched to [REDACTED]) column, then alphabetic order for PTs with the same count. Medical history will be listed on the RAND population.

8.1.7 Prior or Concomitant Medications

The prior will be summarized in table separately by ATC level 2, preferred name and treatment group for the SAF1 and presented in data listing for the RAND population. The concomitant medications that were used based on the start date of use during each period of DBT and DBE will be summarized by ATC level 2, preferred name and treatment group for the SAF1 and SAF2 populations respectively and presented in data listing for the RAND population.

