17. Treatment with antioxidant agents within 4 weeks before Randomization (Visit 2), at doses which, in the opinion of the Investigator, may affect study endpoints (including but not limited to beta-carotene, cysteine, pyridoxine).
18. Chronic treatment with any scheduled analgesic agents including, but not limited to, opioids and opioid derivatives such as morphine, hydrocodone, oxycodone, fentanyl, or their combination with other unscheduled analgesics or non-steroidal anti-inflammatory drug (Percocet and Vicodin-like prescription drugs) within 4 weeks before Randomization (Visit 2). Acute use of scheduled narcotics greater than 3 months prior to randomization, Over the counter (OTC)s, such as Non-steroidal anti-inflammatory drug (NSAID)s or aspirin for analgesia, or prior temporary use of scheduled agents within 3 months of screening are not excluded.
19. Treatment with any drugs or supplements which, in the opinion of the Investigator, can interfere with the objectives of the study or safety of the subjects.
20. Previous exposure to MT-7117 (this does not include placebo treated subjects).
21. Previous treatment with any investigational agent within 12 weeks before Screening OR 5 half-lives of the investigational product (whichever is longer).

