7.2.1.4 Prior or Concomitant Medication

Medications will be coded according to the WHO Drug Dictionary (WHO-DD) B3 MAR 2019 version.

(1) Prior Medication

Prior medications are defined as any medication taken within 1 month before the start date of study drug.

Any prior medication, including prescription and over-the-counter medications, taken within 1 month before Screening will be recorded on the eCRF. Information recorded will include: name of medication, dose, duration of and reason for use. It should be noted if subjects have ever used afamelanotide.

(2) Concomitant Medication

Concomitant medication is defined as any medication, other than study medication, which is taken during the study after the start date of study drug , including prescription, over-the-counter medications, herbals, dietary supplements, and recreational drugs. All concomitant medications taken while the subject is participating in the study will be recorded. Concomitant medication will be given only if deemed necessary by the Investigator or the subject's personal physician.

Rules to determine prior medications and concomitant medications:

Medications with a stop date before the first date of study drug dosing will be considered prior medications. Medications with start date or stop date on or after the first date of study drug dosing or ongoing at study will be considered concomitant medications.

Rule to determine concomitant medication for pain:

If indication in the eCRF for the concomitant medications includes “Pain” or “pain”, the drug was regarded as comitant use for pain.

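### As SAP 8.1.7 is worded, non-prohibited drugs started before first dose and continued on study enter neither concomitant medication table, and drugs carried from DBT into DBE are missing from the DBE table

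*SAP*

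**What the plan says.** SAP 7.2.1.4 describes prior use in two ways. Its opening definition has no stop-date condition: "Prior medications are defined as any medication taken within 1 month before the start date of study drug". The decision rule that follows does have one: "Medications with a stop date before the first date of study drug dosing will be considered prior medications". The same rule defines the other class: "Medications with start date or stop date on or after the first date of study drug dosing or ongoing at study will be considered concomitant". A drug begun before first dose and still being taken is therefore concomitant under the rule, yet also meets the opening definition of prior.

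SAP 8.1.7 sets the tables. For prior drugs: "The prior will be summarized in table separately by ATC level 2, preferred name and treatment group for the SAF1". For concomitant drugs: "The concomitant medications that were used based on the start date of use during each period of DBT and DBE will be summarized", with the same breakdown, "for the SAF1 and SAF2 populations respectively and presented in data listing for the RAND population".

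Four other places bear on the point:
- SAP 7.4 imputes incomplete medication start dates. A completely missing date becomes the first dose date, unless a known stop date is earlier. A missing day becomes the first of the month. A missing day and month become 1 January.
- SAP 8.1.8 gives prohibited medications their own table by treatment, with no start-date condition.
- SAP 8 orders listings by treatment.
- Protocol 10.4 has all concomitant medication recorded throughout participation. It defines prior use as use before Screening, which matches neither SAP statement.

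**The concern.** The decision rule makes an ongoing drug concomitant because of when it stops. The table rule then asks when it started. A drug that began before first dose and continues meets the first test and fails the second, so it is classed as concomitant and tabulated in neither period.

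Long-standing background treatment is the kind of drug that falls into this gap, and the protocol expects some. Exclusion 18 in Protocol 8.4 leaves over-the-counter NSAIDs and aspirin for analgesia unrestricted. Exclusion 17 excludes recent antioxidant use only "at doses which, in the opinion of the Investigator, may affect study endpoints", so lower-dose use may be present. Protocol 8.7.1 accepts established hormonal contraception, which would begin before Day 1 and continue wherever it is recorded as medication.

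What is at stake is description. The trial's key outcomes are patient-reported symptoms and pain, and SAP 7.2.1.4 has its own rule for identifying concomitant drugs taken for pain. A reader who checks whether ongoing analgesic use was similar across arms would look at the concomitant tables, and those would show new starts only.

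**Working it through.** The plan gives no figure to reproduce, so the check is logical. Day 1 is first dose. SAP 7.3 Table 2 gives the nominal periods: DBT is Days 1 to 182 and DBE is Days 183 to 364. For a drug with start day s and stop day e (ongoing means no upper limit), the rules are:

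- Prior, decision rule (7.2.1.4): e < 1.
- Prior, opening definition (7.2.1.4): s < 1 and e ≥ −30, taking one month as 30 days (an assumption).
- Concomitant (7.2.1.4): s ≥ 1 or e ≥ 1.
- DBT table (8.1.7, literal): concomitant and 1 ≤ s ≤ 182.
- DBE table (8.1.7, literal): concomitant and 183 ≤ s ≤ 364.

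Nine constructed patterns, for a subject who enters DBE:

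| Start | Stop | Class by decision rule | 8.1.7 table under decision rule | 8.1.7 table if opening definition sets prior |
|---|---|---|---|---|
| −60 | −40 | prior | prior | none |
| −60 | −5 | prior | prior | prior |
| −60 | 40 | concomitant | none | prior |
| −60 | 200 | concomitant | none | prior |
| −60 | ongoing | concomitant | none | prior |
| 10 | 40 | concomitant | DBT | DBT |
| 10 | ongoing | concomitant | DBT only | DBT only |
| 200 | ongoing | concomitant | DBE | DBE |
| missing, set to 1 | ongoing | concomitant | DBT only | DBT only |

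Three results follow.

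1. Under the decision rule, all three patterns that start before first dose and continue are absent from every 8.1.7 table. Under the opening definition they move to the prior table but are still in neither concomitant table.
2. Five patterns involve use during DBE: −60 to 200, −60 ongoing, 10 ongoing, 200 ongoing, and the missing start. Only the drug started on Day 200 enters the DBE table. This result does not depend on how prior is read.
3. Imputation works in both directions. A completely missing start date is set to Day 1 and counted in DBT. A drug begun after first dose, in the same calendar month and with the day missing, is moved to the first of that month. Unless first dose fell on that date, the drug then starts before Day 1 and drops out.

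Now select by overlap instead: start on or before period end, and stop on or after period start or ongoing. For DBT this is s ≤ 182 and e ≥ 1; for DBE it is s ≤ 364 and e ≥ 183. The −60 to 40 drug enters DBT. The −60 to 200, −60 ongoing, 10 ongoing and missing-start drugs enter both tables. The 10 to 40 drug stays in DBT only and the 200 ongoing drug in DBE only. Every lost pattern is restored.

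**The case against.** The strongest reply is that the loss depends on one reading. The opening definition in 7.2.1.4 would put carried-over drugs in the prior table by arm. The start-date phrase in 8.1.7 is loose and may be meant only to assign each drug to a period, and no table shell is available to settle it. This has force: the loss from the prior table is not certain. It does not remove the problem. Two conflicting statements need reconciling whichever is intended, and assigning by start date gives a drug begun before first dose no period at all.

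A reader might go further and infer that every ongoing drug is lost. The documents do not support that. A completely missing start date is set to first dose and counted, and prohibited drugs have their own table in SAP 8.1.8. Because Protocol Appendix 1 is redacted, one cannot tell how far ongoing antioxidant use is covered there. The NSAID example is the firmer one.

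A reader might also infer that background treatment cannot be compared between arms. That is too strong as well. The data are recorded and listed for all randomized subjects in treatment order. What is missing is a planned summary with counts and percentages.

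On DBE, it is fair to say that showing only new starts could be deliberate and that a drug begun in DBT already appears in the DBT table. The SAP does not state such an intention, however, and the DBE table is presented as concomitant use in SAF2.

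**Conclusion.** The point holds in a limited form. Under the 7.2.1.4 decision rule and the literal wording of 8.1.7, non-prohibited drugs with a start date known or imputed to be before first dose, and continued on study, enter neither concomitant table. They are outside the prior table too unless the opening definition governs. Drugs carried from DBT into DBE are absent from the SAF2 table on either definition of prior.

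The size cannot be given. The shortfall in each table equals the share of drugs in use during the period that began before it, and the documents do not report that share. The nine patterns show which cases are lost, not how often they occur.

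It would be wrong to infer a threat to the efficacy conclusions. No medication table feeds a model, a test or the testing sequence. The primary analysis compares randomized arms on change from baseline with baseline adjustment, and the documents do not show that permitted NSAIDs change time to first prodrome. Only descriptive tables are affected. The wording still merits correction because it contradicts the SAP's own definition of concomitant use, and because the SAP states that it supersedes the protocol on statistical analysis.

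**What to change.** In SAP 7.2.1.4, keep one test for prior use. The simplest course is to let the stop-date rule decide and to drop the one-month sentence or restate it as a recording window. Note the difference from Protocol 10.4.

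In SAP 8.1.7, replace selection by start date with selection by overlap. A medication is summarised as concomitant in a period if it started on or before that period's end and either stopped on or after that period's start or is ongoing. Use each subject's own DBT and DBE dates, and footnote that a drug used in both periods is counted in both tables. With this rule, moving a partial start date earlier no longer removes a drug that is in use.

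Showing pre-dose starts separately from new starts is optional.

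The cost is a short text change and a re-run of the medication tables. No new data are needed and no other analysis changes.

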8.1.8 Prohibited medication

The prohibited medications coded by the protocol Appendix 1 Table 18-1 will be summarized on the SAF1 and SAF2 populations and listed on the RAND population. The summary will be presented by ATC level 2 and preferred name and treatment.

8.1.9 Treatment Duration and Compliance

Treatment duration will be summarized on the ITT1 and ITT2 populations.

Treatment duration and compliance will be listed on the RAND population. Study drug interruptions will be listed on the RAND population.

Compliance to Double-Blind study medication will be presented for the ITT1 and ITT2 population in table by treatment group. The range $80\% \leq \text{compliance} \leq 120\%$ will be used to define a subject being treatment compliant.

The number and percentage of subjects with no study drug suspension, any study drug suspension and permanent study drug discontinuation will be summarized by the DBT period on the ITT1 population and by the DBE period on the ITT2 population.

All study medication administration and accountability data will be listed by subject.

8.1.10 Fitzpatrick skin scale test

The Fitzpatrick skin type will be summarized with number and percentage and the Fitzpatrick total score will be summarized by treatment group and analysis visit for the ITT1 and ITT2

populations.

8.1.11 Subject Questionnaire for Study Medication

Subject questionnaire for study medication will be summarized and listed.

8.2 Efficacy Assessments

All efficacy endpoints will be analysed under primary estimand unless otherwise stated.

All data will be listed.

For DBT data analysis

All efficacy endpoints in Section 2.3.1, 2.3.2, and 2.3.3 will be summarized using descriptive statistics or using the number with percentage in the ITT1 population. All of the statistical model analyses stated in the below sections will be done in the ITT1 only for DBT data analysis only.

8.2.1 Primary Efficacy Endpoint

Primary Analysis

For the ITT1 population, the primary estimand will be tested including retrieved dropout data (after treatment discontinuation), using treatment comparisons of interest in change from baseline in average daily time to first prodromal symptom associated with exposure to sunlight between 1 hour post sunrise and 1 hour pre-sunset for the two MT-7117 doses (█ and █ █) compared with placebo at Week 26 (Visit 7).

To assess the treatment effect at Week 26, change from baseline in average daily time (minutes) to first prodromal symptom associated with exposure to sunlight between 1 hour post sunrise and 1 hour pre-sunset at Weeks 2, 4, 6, 8, 10, 12, 14, 16, 18, 20, 22, 24, and 26 will be analyzed using mixed-effect model for repeated measures (MMRM). The model will include fixed categorical terms for treatment, █

█ visit, and treatment by visit interaction together with continuous covariate terms for baseline average daily duration of sunlight exposure between 1 hour post sunrise and 1 hour pre-sunset to first prodromal symptom and baseline average daily duration of sunlight exposure between 1 hour post sunrise and 1 hour pre-sunset to first prodromal symptom by visit interaction. An unstructured (UN) correlation structure will be used to model the within-subject variance covariance errors. Should convergence of the model fail (due to the small numbers of

subjects in this study), the heterogeneous compound symmetry (CSH) and the heterogeneous Toeplitz structure (TOEPH), autoregressive [AR(1)] and compound symmetry (CS) correlation matrix will be used in that order instead of UN. The Kenward-Roger approximation will be used to estimate the denominator degrees of freedom. From the model described above, adjusted (least squares [LS]) means and standard errors will be produced by treatment group and visit. Difference in adjusted means at each visit (each MT-7117 dose vs. placebo) with standard errors, 95% CIs and associated p-values will also be produced. All available data from all subjects will be used in the primary analysis without any imputation.

Sensitivity Analysis

(1) Use of actual strata of baseline average daily sunlight exposure time to first prodromal symptom for randomization registration errors

In the above primary analysis model, [REDACTED]

[REDACTED] directly derived from e-Diary raw dataset.

(2) Controlled multiple imputation method

The primary analysis model is using likelihood based approach to handle missing data under Missing At Random (MAR) missingness pattern in the primary estimand. In order to assess the robustness of the primary analysis also under Missing Not At Random (MNAR) pattern, a control group-based multiple imputation (MI) of the Pattern Mixture Model (PMM) method will be used. This model assumes MNAR for missing data mechanism in MT-7117 [REDACTED] and [REDACTED] and MAR for missing data mechanism in placebo on the ITT population.

- Step 1: This methodology will structure data based on missing data patterns. The PMM method will be based on a missingness pattern having a monotone structure, i.e. if among the observations over time one data value is missing, all other values after this missing value will also be missing. For patients with intermittent missing values, before performing MI based on the PMM, it will be necessary to create a monotone missingness pattern. Intermittent missing values will be imputed using the Markov Chain Monte Carlo (MCMC) methodology which assumes a multivariate normal distribution over all variables included in the imputation model. The MI procedure in SAS will be used for this purpose and this first MI step is planned to be repeated 100 times, creating different datasets with a monotone missing data structure. Seed value of 2022 will be used in the MI procedure. The imputation with the explanation variables of the baseline value and the post-baseline values is based on the MAR assumption, i.e. the missing data are assumed to follow the same model as the other patients. The minimum number

will be set as 0 because the imputed value for time to first prodromal symptom should be greater than or equal to 0.

The following SAS code will be used to generate the monotone missing data pattern:

[REDACTED]

- Step 2: After this, the remaining missing data will be imputed using a MI method for monotone missingness, with the assumption that the data on MT-7117 [REDACTED] and [REDACTED] once daily groups are MNAR and the data on placebo group are MAR. Control group-based assumption will be used for the missing data. Thus, for each of the created dataset with a monotone missing data pattern in step 1, the MI procedure in SAS will be used to impute missing values based on a sequential procedure reflecting the monotone missing data pattern. The MNAR statement of the following (see SAS code) will be used to generate the imputation.

Patients with the first missing value occurring at Week 2 (“W2”) will have their missing Week 2 value replaced by an imputed value from a regression model with [REDACTED]

[REDACTED] and the baseline value (BASE) as explanatory variables. In the next step, patients with their Week 4 (“W4”) value missing will have their missing Week 4 value replaced by an imputed value from a regression model with baseline average daily first to prodromal symptoms and the Week 2 value as explanatory variables. Similar procedure will be used to replace the missing values at week 4, 6, 8 and 10 etc. [REDACTED]

[figure not shown]
[REDACTED] If the imputed value is less than 0 and then the value will be replaced with 0.

The following SAS code for the missing data imputation at Week 26 will be used to make the imputation with the MNAR assumption:

[REDACTED]

- Step 3: The imputed dataset (IMPUTED) generated with the approach described above do contain only non-missing values. MMRM model similar to that described for the primary analysis will thus be run on each of the 100 generated imputed datasets and the differences between the treatment groups at Week 26 will be estimated (and export to data 'ESTIMATES'). Finally, the MIANALYZE procedure in SAS will be applied to combine the results from these analyses to derive an overall estimate of the treatment differences at W26. In addition to the estimates, corresponding 95% confidence intervals and p-values will be calculated.

The following example SAS code will be used:

(3) Non-parametric analysis

Non-parametric analysis will be performed in order to confirm the robustness for the above parametric model. The change from baseline in average daily time (minutes) to first prodromal symptom associated with exposure to sunlight between 1 hour post sunrise and 1 hour pre-sunset at each visit (Weeks 2, 4,..., 24, and 26) from two treatments being compared will enter the corresponding analysis. The point estimates and two-sided 95% confidence intervals for the difference between the treatment groups will be obtained using the Hodges-Lehman estimator corresponding to Wilcoxon's rank sum test. The paired comparison between each MT-7117 arm with placebo will also be performed using this non-parametric analysis method. This non-parametric analysis will be performed with multiple imputation (MI) method in the following steps, assuming missing at random.

- MI Step 1: Intermittent missing values will be imputed using the Markov Chain Monte Carlo (MCMC) methodology which assumes a multivariate normal distribution over all variables included in the imputation model. The MI procedure in SAS will be used for this purpose and

this first MI step is planned to be repeated 100 times, creating different datasets with a monotone missing data structure. Seed value of 2022 will be used in the MI procedure. The minimum number will be set as 0 because the imputed value for time to first prodromal symptom should be greater than or equal to 0.

The following SAS code will be used to generate the monotone missing data pattern:

- MI Step 2: After this, the remaining missing data will be imputed using a method for monotone missingness, also based on the MAR assumption. Thus, for each of the created dataset with a monotone missing data pattern, the MI procedure in SAS will be used to impute missing values based on a sequential procedure reflecting the monotone missing data pattern. Subjects with the first missing value occurring at Week 2 will have their missing Week 2 value replaced by an imputed value from a regression model with treatment group (trtp),

and the baseline value (base) as the explanatory variables. In the next step, subjects with their Week 4 value missing will have their missing Week 4 value replaced by an imputed value from a regression model with treatment group, the randomization strata, baseline value and Week 2 value as explanatory variables. Similar procedure will be used to replace the missing values at Week 4, 6, ..., 24, and 26. If the imputed value is less than 0 and then the value will be replaced with 0.

The following example SAS code will be used to make the imputation with the MAR assumption:

- MI Step 3: The imputed datasets generated with the approach described above do contain only non-missing values and are used as input in the model for the sensitivity analysis for the primary efficacy endpoint. For the difference between the treatment groups with paired comparison

(MT-7117 [REDACTED] vs. Placebo and MT-7117 [REDACTED] vs. Placebo) in Week 2, 4, ..., 24, and 26, the Hodges-Lehman estimator and asymptotic standard error of this estimator will be calculated on each of the 100 generated imputed datasets, using the NPAR1WAY procedure in SAS. Finally, the MIANALYZE procedure in SAS will be applied to combine the results from these analyses to derive an overall estimate of the treatment differences at Week 2, 4, ..., 24, 26 according to the following code. In addition to the estimates, corresponding 95% confidence intervals and p-values will be calculated.

The following example SAS code will be used:

[REDACTED]
[REDACTED]
[REDACTED]
[REDACTED]
[REDACTED]
[REDACTED]

(3) LOCF imputation analysis

For this primary endpoint, ANCOVA with treatment group (trtp), [REDACTED]

[REDACTED] and the baseline value as the explanatory variables will be also performed. For missing data for the primary endpoint, LOCF approach assuming MNAR will be used to impute this missing data.

(4) Impact of removing the 3 subjects (USUBJID: [REDACTED], [REDACTED] and [REDACTED], [REDACTED], See the detail in the DRM minutes) with ICH E6 GCP violation (Lost of source document).

These three subjects data will be removed from the primary endpoint and the above primary analysis model will be performed.

Supportive Analysis

The secondary estimand will use similar estimator as for the primary analysis. The ITT1 population with the primary efficacy data without retrieved dropout data (after treatment discontinuation) will be used for this analysis. Likelihood based model method under Missing at Random assumption will be performed using the same MMRM as specified for the primary analysis. The only primary endpoint will be also analyzed in the secondary estimand and the other efficacy endpoints will not be analyzed in this estimand.

Multiplicity adjustment for treatment comparison on primary and secondary endpoints

The overall study-wise type I error will be 5%. Type I error will be globally strongly controlled by employing the fixed sequence approach, (i.e., each endpoint will be formally analyzed only in case the preceding endpoint will have a p-value less than or equal to 0.05).

To protect the study from type I error inflation, the lower ordered comparison will be interpreted inferentially only if a statistically significant treatment effect is detected in the higher ordered comparison ($H1 \Rightarrow H2, \dots, H11 \Rightarrow H12$). The following null hypothesis will be sequentially tested via the following order;

H1: There is no treatment difference between MT-7117 [REDACTED] and placebo in change from baseline in average daily time (minutes) to first prodromal symptom associated with exposure to sunlight between 1 hour post sunrise and 1 hour pre-sunset at Week 26.

H2: There is no treatment difference between MT-7117 [REDACTED] and placebo in change from baseline in average daily time (minutes) to first prodromal symptom associated with exposure to sunlight between 1 hour post sunrise and 1 hour pre-sunset at Week 26.

H3: There is no treatment difference between MT-7117 [REDACTED] and placebo in PGIC at Week 26.

H4: There is no treatment difference between MT-7117 [REDACTED] and placebo in PGIC at Week 26.

H5: There is no treatment difference between MT-7117 [REDACTED] and placebo in total number of sunlight-induced pain events defined as prodromal symptoms (burning, tingling, itching, or stinging) with pain rating of 1-10 on the Likert scale during 26-week double-blind treatment period.

H6: There is no treatment difference between MT-7117 [REDACTED] and placebo in total number of sunlight-induced pain events defined as prodromal symptoms (burning, tingling, itching, or stinging) with pain rating of 1-10 on the Likert scale during 26-week double-blind treatment period.

H7: There is no treatment difference between MT-7117 [REDACTED] and placebo in change from baseline for total score in the domain of pain intensity in the PROMIS-57 at Week 26.

H8: There is no treatment difference between MT-7117 [REDACTED] and placebo in change from baseline for total score in the domain of pain intensity in the PROMIS-57 at Week 26.

H9: There is no treatment difference between MT-7117 [REDACTED] and placebo in the percentage of subjects who are responders at Week 26 based on average daily sunlight exposure time to first prodromal symptoms using the within-subject meaningful change of 66 minutes increase.

H10: There is no treatment difference between MT-7117 [REDACTED] and placebo in the percentage of subjects who are responders at Week 26 based on average daily sunlight exposure time to first prodromal symptoms using the within-subject meaningful change of 66 minutes increase.

H11: There is no treatment difference between MT-7117 [REDACTED] and placebo in change from

baseline for total score in the domain of physical function in the PROMIS-57 at Week 26.

H12: There is no treatment difference between MT-7117 [REDACTED] and placebo in change from baseline for total score in the domain of physical function in the PROMIS-57 at Week 26.

Subgroup Analysis

The consistency of treatment effect on the primary endpoint across different subgroups will be explored based on the ITT1 population and the primary estimand for the following subgroups using the primary efficacy analysis.

- Gender (Male, Female)
- Age group (age <18, 18=< age)
[REDACTED]
- Ethnicity (Hispanic or Latino, Non-Hispanic or Latino, Others)
- Race (White, Black or African American, Asian(Japanese), Others)
- BMI (BMI <30, BMI \geq 30 kg/m²)
[REDACTED]
[REDACTED]
- Seasonality1 (Randomized in Spring and Summer inclusive, Other)
- Seasonality2 (Week 26 visit in Spring and Summer inclusive, Other)
- Average melanin density at BL (>=Median, <Median)
- Fitzpatrick scale test category (I-II or III-VI)
- Protoporphyrin (>=Median, <Median)
- Porphyrin (>=Median, <Median)
- EPP vs XLP
[REDACTED]
[REDACTED]
[REDACTED]
[REDACTED]
[REDACTED]
- Study Drug Compliance by Week 26 (no study drug suspension, any suspension or permanent study drug discontinuation)

Bayesian analysis for adult and adolescent subgroups

Age group (age <18, 18=<age)

In order to estimate treatment effects for adult and adolescent for the primary endpoint, Bayesian subgroup hierarchical model and Commensurate prior model will be performed using both adolescent and adult subgroup data in order to get greater precision on treatment effect

and address random high and random low data values due to small sample estimates. This means these analysis does not estimate treatment effect within adolescent subgroup in isolation of adult subgroup. Details of the model and the framework can be found in Appendix 1. The posterior means, SE and 95% Credible Interval(CrI) for the primary endpoint will be presented for each treatment group. The posterior mean, SE and 95% CrI will be obtained for the difference of each of the active MT-7117 treatment groups versus placebo. In addition, the probability that the difference in the primary endpoint versus placebo > 0 will be presented for MT-7117 [REDACTED] and [REDACTED], respectively. If this probability is at least greater than 95%, then this will be considered as “a statistically significant difference” for the active dose and the subgroup. If the posterior mean for the difference in the primary endpoint versus placebo will be greater than 0 in both adult and adolescent subgroups in the MT-7117 active dose, then this will be considered as “a positive trend” for the active dose among the subgroups.

Funnel plot analysis

In order to confirm the relation between change from baseline for the average potential outliers of treatment effect by site and by country for the primary endpoint, funnel plot analysis by site and by country will be performed respectively. The curves on the graph delineate overall mean treatment difference (MT-7117 [REDACTED] – Placebo, MT-7117 [REDACTED] – Placebo) plus/minus 2*standard error limits [$Z(0.05/2) \times$ overall standard deviation (SD) $\times \text{sqrt}(2/n)$, Note: $Z(0.05/2) = \text{quantile}("Normal", 0.975)$]. Overall SD will be SD for overall in the calculated two treatment groups and n will be determined (e.g. 1 to 15) based on average sample size per treatment group in the calculated two treatment groups in each site and each country.

